8.3.4 SERIOUS ADVERSE EVENT REPORTING

All AEs and SAEs that occur throughout the study, whether study-related or non-related, will be documented and reported to the IRB, as per IRB regulations. AE/SAE report forms will be completed within 48 hours throughout the study for each participant. We will keep a running log of all AE/SAEs (anticipated and unanticipated) throughout the study. Any SAE will be reported to the IRB within 24 hours, and the study will be suspended until the study physician states that it is safe to resume the study.

9 STATISTICAL CONSIDERATIONS

9.1 SAMPLE SIZE DETERMINATION

All statistical tests will be 2-sided. The outcome measures will be tested at a 0.05 level of significance. SPSS will be used to conduct the statistical analyses. All participants who have EAW sessions will be included (regardless of the number of sessions they complete before discharge, but the number and reason of missing EAW sessions will be recorded). To test the three main hypotheses of the proposed study, the change score of each outcome between baseline and discharge will be calculated. The change score will be compared between the intervention and control groups using independent t-test analyses (if the outcomes are not normally distributed, Mann-Whitney tests will be used).

Since the primary aim of the study is to compare the improvement of FIM scores between the groups, the FIM score results from the preliminary data were used to perform the power analysis for this study. In the preliminary data, the mean change in FIM score from the intervention group was 35 ± 12 , and the control group was 22 ± 13 . The effect size of the FIM score change in our preliminary data was 1.07 (controlling for the different number of participants between the two groups). The power analysis showed that using the effect size (1.07) and 0.05 level of significance with two-sided analysis in independent t-test, a total of 30 participants will provide the study 80% power.

To account for an expected attrition rate of about 25%, 40 participants will be enrolled. It is expected that 30 participants will complete the study (the reasons and number of screening failures and dropouts will be recorded).

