6 STUDY INTERVENTION

6.1 STUDY INTERVENTION(S) ADMINISTRATION

6.1.1 STUDY INTERVENTION DESCRIPTION

Intervention (N=20): In the intervention group, participants will receive locomotor training provided with an Ekso™ powered exoskeleton according to the standard of care of AIR at Mount Sinai Hospital with the exception that the EAW training will be incorporated into the designated therapy times (3 hours of physical therapy (PT) and/or occupational therapy (OT)) which will be provided as determined by the clinical team from the earliest time they are identified to be able to safely stand, through discharge. The goal of EAW intervention is to complete three or more sessions of EAW training a week during the AIR period (after enrolling into the study until discharge). One EAW session is defined to have at least 20 minutes of uptime in the device (based on data output from EksoTM, device, not including donning and doffing time). EAW sessions will include device fitting, instruction for sit-to-stand and stand-to-sit maneuvers; balance and fall protection training; and walking on smooth indoor surfaces with total or variable device assistance. The clinical team will determine the frequency, duration, and intensity of each EAW session based on the participant's response to the previous session.

Control (N=10): In the control group, participants will receive standard of care AIR which includes three hours of PT and/or OT per day until they are discharged. This standard of care AIR may include bed mobility, balance, strength, gait, transfers, and wheelchair mobility training to improve participants' independence in activities of daily living, such as bathing, eating, dressing, grooming, and wheelchair use but does not include EAW. The two groups (control and intervention) will have the same total amount of therapy time.

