6.2 MEASURES TO MINIMIZE BIAS: RANDOMIZATION AND BLINDING

Eligible participants will be randomized into either the intervention group or the control group. In order to provide more opportunities for participants to accept EAW training, the intervention group will have 20 participants, and the control group will have 10 participants.

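### Section 9.1's 80% power reproduces only with equal or near-equal groups; at the planned 20:10 split, 30 completers give 76.0%

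*Combined protocol and SAP*

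**What the plan says.** Section 9.1 bases the sample size on the change in FIM score. The preliminary data gave a mean change of 35 (SD 12) with the intervention and 22 (SD 13) without it, and the section reports a standardised effect of 1.07. It specifies a "0.05 level of significance with two-sided analysis in independent t-test" and concludes that "a total of 30 participants will provide the study 80% power". No ratio between the groups is given for that calculation. The section's one remark about unequal numbers is attached to the effect size from the preliminary data.

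The same section allows for attrition of about 25% by enrolling 40, and adds: "It is expected that 30 participants will complete the study".

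The allocation appears elsewhere. Section 6.2 says "the intervention group will have 20 participants, and the control group will have 10 participants", so that more participants can be offered exoskeletal walking. Section 6.1.1 gives the same group sizes. Neither section says whether these are participants randomised or participants completing.

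**The concern.** For a fixed total, a two-sample t-test has most power when the groups are equal. A power figure quoted for 30 participants therefore means little until the split is known, and 9.1 does not give it. If 80% holds for equal groups, it is too high for the 2:1 design that 6.1.1 and 6.2 describe.

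This figure is the plan's whole justification for its sample size. Someone reading a non-significant FIM result would rely on it to judge how likely the trial was to detect the effect it was planned around.

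**Working it through.** **Inputs.** From 9.1: d = 1.07, α = 0.05 two-sided, independent t-test, 30 completers, 25% attrition. From 6.1.1 and 6.2: 20 intervention and 10 control. The 20 and 10 are read as completers because 20 + 10 = 30, the number 9.1 expects to complete.

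**Formula.** Exact power of the pooled t-test from the noncentral t distribution, with df = n1 + n2 − 2 and noncentrality λ = d × √(n1·n2/(n1 + n2)). Power is the probability that |T| exceeds the two-sided 5% critical value, which is 2.048 for df = 28.

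**The plan's own figure.** With 15:15, λ = 1.07 × √(225/30) = 1.07 × 2.739 = 2.930 and power is 80.7%. With 14:14 it is 77.8%, so 30 is the smallest total with equal groups that reaches 80%. The stated figure therefore reproduces under equal allocation.

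**The planned split.** With 20:10, λ = 1.07 × √(200/30) = 1.07 × 2.582 = 2.763 and power is 76.0%.

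| Split of 30 | λ | Power |
|---|---|---|
| 15:15 | 2.930 | 80.7% |
| 16:14 | 2.924 | 80.6% |
| 17:13 | 2.904 | 80.0% |
| 18:12 | 2.871 | 79.1% |
| 19:11 | 2.824 | 77.8% |
| 20:10 | 2.763 | 76.0% |

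**Detectable effect.** At 20:10, 80% power requires d = 1.124; at 15:15 it requires 1.060. The SD implied by 9.1 is 13/1.07 = 12.15 FIM points (derived here, not stated in the plan). The effect detectable at 20:10 is then 1.124 × 12.15 = 13.7 points, against the assumed difference of 35 − 22 = 13.

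**Size needed for 80% at exactly 2:1.** With 22:11, df = 31, λ = 1.07 × √(242/33) = 2.898 and power is 80.1%. That is 33 completers. Enrolment at 25% attrition is 33/0.75 = 44, against 30/0.75 = 40 as planned.

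**Sensitivity to the effect size.** The preliminary group sizes are not reported, so 1.07 cannot be rebuilt exactly from the rounded SDs. Results at 20:10:

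- SDs weighted 1:1: d = 13/√((144 + 169)/2) = 1.039, power 73.6%.
- SDs weighted 2:1: d = 13/√((2×144 + 169)/3) = 1.053, power 74.7%.
- Outer limits, using one SD alone: d = 13/13 = 1.00, power 70.3%; d = 13/12 = 1.083, power 77.0%.

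None of these reaches 80%.

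**The case against.** - **The ratio behind 9.1 is an inference.** The section states none, and a normal approximation at 20:10 gives 78.9%, which might loosely be called 80%. The first part stands: the text does not say that equal groups were assumed. The second is weak. Section 9.1 names the t-test, the normal approximation overstates t-test power at this size, and its own minimum total is 28 at 1:1 or 33 at 2:1, not 30. In any case the 76.0% does not depend on how the 80% was obtained.

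- **Section 9.1 already mentions controlling for different group numbers.** That remark qualifies the effect size from the preliminary data, not the allocation of this trial. With 1.07 taken as given, 20:10 still yields 76.0%.

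- **20 and 10 may not be completers.** This is a real ambiguity, but the other reading is worse for the plan. If 20 and 10 are randomised and a quarter drop out, about 15 and 8 remain (10 × 0.75 = 7.5, rounded up), and power is about 64%.

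- **Four points is small beside the uncertainty in 1.07, and 2:1 was chosen deliberately.** Both are true. Section 6.2 gives a legitimate reason for the unequal split. They limit how much weight the point carries, but they do not make the stated figure right.

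**Conclusion.** The concern holds. At the plan's own effect size, test and significance level, 20 and 10 completers give 76.0% power, 4 points below the stated 80%. The probability of missing the assumed effect is 24.0%.

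This rests on d = 1.07 as stated, the pooled t-test named in 9.1, and 20 and 10 being completers. The shortfall is modest, but it lies in the figure that justifies the sample size, so it should be corrected. The choice of 2:1 is not itself in question.

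**What to change.** In 9.1, name the allocation and restate the power. Suggested wording: *With 2:1 allocation (20 intervention and 10 control completers), an effect size of 1.07 and a two-sided 0.05 independent t-test, power is about 76% (80% for an effect size of about 1.12).*

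In 6.1.1 and 6.2, say what 20 and 10 count. Target completers is the reading that agrees with the 30 in 9.1; the sponsor should confirm it.

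In 9.1, state how the 40 enrolled divide between screening failures and the two arms, since the section takes both kinds of loss together ("the reasons and number of screening failures and dropouts will be recorded"). If all 40 were randomised 2:1, the split would be about 27:13, but that is an assumption.

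The cost is wording in three sections and a slightly less favourable power figure. No patients are added. Keeping 80% at an exact 2:1 ratio is optional and would take 33 completers and 44 enrolled, 4 more than planned.

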7 STUDY INTERVENTION DISCONTINUATION AND PARTICIPANT DISCONTINUATION/WITHDRAWAL

7.1 DISCONTINUATION OF STUDY INTERVENTION

Subjects may be withdrawn without their consent if it is found that they do not meet eligibility criteria for the study, or if during an exoskeleton instruction session, research staff or clinicians have concerns about the participant's performance or safety and feel that discontinuing involvement would be in the best interest of the participant.

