7.2 PARTICIPANT DISCONTINUATION/WITHDRAWAL FROM THE STUDY

If subjects decide to stop being in the research study, they can contact the Principal Investigator or the research staff. There are no early withdrawal procedures that will be required of participants.

Participants may also withdraw their permission for the use and disclosure of any of their protected information for research, but they must do so in writing to the Principal Investigator at the address on the first page. Even if they withdraw their permission, the Principal Investigator for the research study may still use the information that was already collected if that information is necessary to complete the research study. Their health information may still be used or shared after their withdraw their authorization if they have an adverse event from participating in the research study.

If they decide they don't want their samples and/or data to be used for research anymore, they can contact the researcher and ask to have their samples and/or data removed from future use. If any samples or data have already been shared without their identity, it won't be possible to retrieve them because no one will know who they are.

Samples and data that have already been used will not be affected by their decision. Any samples and/or data that are still linked to their identity by a code the researcher has will be withdrawn so that no future sharing of their samples and/or data will take place. If their samples have already been deposited in an external repository, the study team will request that their samples be removed.

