9.2 STATISTICAL ANALYSES

9.2.1 GENERAL APPROACH

All statistical tests will be 2-sided. The outcome measures will be tested at a 0.05 level of significance. SPSS will be used to conduct the statistical analyses. All participants who have EAW sessions will be included (regardless of the number of sessions they complete before discharge, but the number and reason of missing EAW sessions will be recorded). To test the three main hypotheses of the proposed study, the change score of each outcome between baseline and discharge will be calculated. The change score will be compared between the intervention and control groups using independent t-test analyses (if the outcomes are not normally distributed, Mann-Whitney tests will be used).

In addition to the primary analysis, several secondary analyses will be performed. 1) Each of the outcomes will be compared between pre- and post-EAW training using a paired t-test analysis (if the outcomes are not normally distributed, Wilcoxon signed-rank test will be used). 2) Analyses will be performed to determine the relationships between the change of outcome measures and EAW training time (including sessions, up time, walking time, or total number of steps per session and across all sessions) using correlation coefficients, regression analyses (stepwise and logistic), analyses of covariance, and nonparametric analyses as appropriate. 3) An additional exploratory post

hoc analyses will be to determine the relationship of participant's baseline characteristics with successful use of the exoskeleton. This post hoc analysis would serve as pilot data to begin to determine who is a good candidate for EAW training during AIR for a future study.

References:

1. Simpson, L.A., et al., *The health and life priorities of individuals with spinal cord injury: a systematic review*. J Neurotrauma, 2012. **29**(8): p. 1548-55.
2. Ditunno, P.L., et al., *Who wants to walk? Preferences for recovery after SCI: a longitudinal and cross-sectional study*. Spinal Cord, 2008. **46**(7): p. 500-6.
3. Tate, D.G., C.Z. Kalpakjian, and M.B. Forchheimer, *Quality of life issues in individuals with spinal cord injury*. Arch Phys Med Rehabil, 2002. **83**(12 Suppl 2): p. S18-25.
4. [name], T.N. and K.T. Ragnarsson, *Pain after spinal cord injury*. Phys Med Rehabil Clin N Am, 2000. **11**(1): p. 157-68.

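### Inclusion tied to EAW sessions, a withdrawal trigger that only the EAW arm can meet, and no assessment at exit can drop randomised participants from the primary comparison, most plausibly in favour of EAW

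*Combined protocol and SAP*

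**What the plan says.** - **Size and attrition (9.1).** Forty are enrolled to allow for about 25% attrition: "It is expected that 30 participants will complete the study". That total matches the 20 intervention and 10 control participants in 6.1.1 and 6.2. The same paragraph says that screening failures and dropouts will be recorded.
- **Analysis (9.1 and 9.2.1, same text).** Baseline-to-discharge change is compared between arms by t-test, or by Mann-Whitney test if the outcome is not normal. The only inclusion rule is "All participants who have EAW sessions will be included", however few sessions they complete. Nothing is said about people randomised to EAW who have no session, about controls, or about missing discharge scores. No intention-to-treat set is named.
- **Withdrawal by staff (7.1).** Apart from ineligibility, participants may be withdrawn "if during an exoskeleton instruction session, research staff or clinicians have concerns" about performance or safety and judge that stopping is in the participant's best interest.
- **At exit (7.2).** "There are no early withdrawal procedures that will be required of participants".
- **Loss to follow-up (7.3).** Marked N/A.
- **Control arm (6.1.1).** Standard inpatient rehabilitation without EAW.

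**The concern.** Three provisions act together. A change score needs a discharge value. One staff-initiated route out of the trial can be triggered only in the EAW arm, and it is partly tied to how well the participant performs. Nothing requires the discharge assessment to be done for people who take that route. If judged performance predicts FIM gain, the EAW participants who remain are a favourable subset, while the controls are not filtered in the same way.

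There is a possible second route. Under 6.1.1, EAW begins only once the clinical team judges that the participant can stand safely. Someone randomised to EAW who never reaches that point has no session and is not covered by the inclusion sentence. A control with the same course faces no such filter.

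At stake is the randomised comparison itself. With about 30 people analysed, a few selective losses can shift the estimated effect, and discharge scores not collected before the participant leaves hospital cannot be recovered.

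**Working it through.** **1. The plan's own figures.**
- Enrolment: 30 / (1 − 0.25) = 40, which matches.
- Power: inputs are "The effect size of the FIM score change in our preliminary data was 1.07", "All statistical tests will be 2-sided" and a 0.05 level; the stated result is "a total of 30 participants will provide the study 80% power". The noncentral t gives 80.7% with 15 per arm and 76.0% with the planned 20:10. That gap is a separate matter.
- Preliminary FIM difference: 35 − 22 = 13 points, used as the yardstick below.

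**2. Who can be lost, by arm.**

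| Route out of the comparison | EAW | Control |
|---|---|---|
| Found ineligible (7.1) | yes | yes |
| Own decision to leave (7.2) | yes | yes |
| Staff concern in an exoskeleton session (7.1) | yes | cannot occur |
| No EAW session, so outside the inclusion sentence (9.1, 9.2.1) | possible | not applicable |

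**3. Size of the bias if the EAW-only route selects on outcome.** The documents give no dropout by arm or by outcome, so these inputs are assumptions:
- no true effect;
- SD of FIM change 13 (the preliminary control SD; the intervention SD was 12);
- 40 randomised 2:1, about 27:13;
- the k lowest of 27 EAW participants on judged performance are withdrawn without a discharge score, and no control is lost;
- correlation ρ between judged performance and FIM change.

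Bias = ρ × SD × m, where m is the expected mean of the largest 27 − k of 27 standard normal values: m = 0.2027 for k = 3 and 0.4226 for k = 7.

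| k | ρ | Bias (FIM points) | Type I error (simulated) |
|---|---|---|---|
| 3 | 0.3 | 0.3 × 13 × 0.2027 = 0.8 | 5.3% |
| 3 | 0.5 | 0.5 × 13 × 0.2027 = 1.3 | 6.3% |
| 3 | 0.7 | 0.7 × 13 × 0.2027 = 1.8 | about 8% |
| 7 | 0.3 | 0.3 × 13 × 0.4226 = 1.6 | 6.5% |
| 7 | 0.5 | 0.5 × 13 × 0.4226 = 2.7 | 10.0% |
| 7 | 0.7 | 0.7 × 13 × 0.4226 = 3.8 | 15.3% |

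Simulated biases agree with the formula to within 0.1 point. Against the 13-point difference, k = 3 gives 6% to 14% (0.8/13 to 1.8/13) and k = 7 gives 12% to 29% (1.6/13 to 3.8/13).

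**4. Other loss patterns** (27:13 reduced to 20:10, SD 12.5, no true effect).
- Random loss in both arms: bias 0.0, type I error 5.2%.
- Low improvers leave EAW, controls lost at random: +1.6 points (6.4%) at ρ = 0.3 and +2.6 (9.4%) at ρ = 0.5.
- Same selection in both arms, ρ = 0.5: +0.3 points (6.0%).
- High improvers leave EAW, ρ = −0.5: −2.6 points.
- Low improvers leave the control arm only, ρ = 0.5: −2.3 points.

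**5. If only 30 are randomised (20:10) and 2 of 20 EAW participants are withdrawn** (SD 13): 0.7, 1.2 and 1.7 points at ρ = 0.3, 0.5 and 0.7, with type I error of 5.7%, 5.8% and 7.0%.

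**The case against.** Several stronger readings are tempting, and the documents do not support them.

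- **That the plan chooses a completer analysis of 30.** It never says so. The figure of 30 is a projection in the sample-size section, and the inclusion sentence keeps EAW participants who attend few sessions. What stands is narrower: that sentence protects people with low attendance but cannot supply a missing discharge score.
- **That the result is biased toward EAW.** Direction and size depend on who leaves and why, which the documents do not report. Random or symmetric loss gives almost no bias, and opposite selection reverses it.
- **That poor performers are removed from the study.** Section 7.1 covers performance or safety and requires a best-interest judgement. Its heading concerns stopping the intervention, while its text speaks of withdrawing subjects and ending their involvement, so whether they leave the study is ambiguous. Withdrawals for safety may also be less closely related to FIM gain.
- **That 25% of the EAW arm is lost after randomisation.** Consent precedes screening (5.3, 8.2), and 9.1 mentions screening failures alongside dropouts. Some or all of the 25% may be lost before randomisation, which cannot bias the arms. Section 6.2 can also be read as randomising only 30. The scenario with 7 of 27 is therefore at the upper end, and it leaves 20 + 13 = 33 analysed rather than 30.
- **That N/A in 7.3 shows neglect.** Participation ends at inpatient discharge, so this is weak evidence.

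These points limit the size and certainty of the bias. They do not remove the one-arm trigger, the absence of an exit assessment, or the lack of an analysis set based on randomised arm.

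**Conclusion.** The point holds in conditional form. Followed as written, the plan can lose randomised participants from the EAW arm by a route that controls do not have, and that route is partly linked to performance. This can bias the primary comparison, most plausibly toward EAW.

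The likely scale is modest with few withdrawals: with 3 of 27, type I error is about 5% to 8%. It is material with 7 of 27, where type I error is about 6% to 15%. Both ranges assume ρ between 0.3 and 0.7, SD 13, 27:13 randomised and no control losses. The withdrawal fraction and ρ drive the result, and neither can be taken from the documents. That the bias exists, or that it favours EAW, is not established.

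**What to change.** - **7.1 and 7.2:** State that stopping EAW is not leaving the study; the decision to stop EAW stays with the clinicians. Unless consent is withdrawn, collect the planned discharge FIM, SCIM and ISNCSCI for every randomised participant.
- **9.1 and 9.2.1:** Replace the inclusion sentence with analysis of all randomised participants by assigned arm, including those randomised to EAW who had no session. Add a simple missing-data sensitivity analysis for those without discharge scores. Multiple imputation and a tipping-point analysis are options, but a trial with so few controls does not require either in particular.
- **9.1:** Say how much of the 25% is expected before and how much after randomisation, and report losses by arm with reasons.

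The cost is protocol wording plus a few discharge assessments, done while participants are still inpatients. The effect estimate may be diluted by people who stopped EAW. If all 40 were randomised 27:13 and scored, power at an effect size of 1.07 would be 87.0% by the noncentral t. If the effect were diluted by 25% (1.07 × 0.75 = 0.80), it would be 63.9%.
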